8.4. Disease-Related Events and/or Disease-Related Outcomes Not Qualifying as SAEs

An event which is part of the natural course of the disease under study (i.e., disease progression or hospitalization due to disease progression) does not need to be reported as a serious adverse event (SAE). Death due to disease under study is to be recorded on the Death electronic case report form (eCRF). However, if the underlying disease (i.e.,

CONFIDENTIAL

progression) is greater than that which would normally be expected for the subject, or if the investigator considers that there was a causal relationship between treatment with study treatment(s) or protocol design or procedures and the disease progression, then this must be reported as a SAE.

8.5. Time Period and Frequency of Detecting AEs and SAEs

The investigator or site staff is responsible for detecting, documenting and reporting events that meet the definition of an adverse event (AE) or serious adverse event (SAE).

AEs will be collected from the time the first dose of study treatment is administered until 30 days following discontinuation of study treatment regardless of initiation of a new cancer therapy or transfer to hospice.

SAEs will be collected over the same time period as stated above for AEs. In addition, any SAE assessed **as related** to study participation (e.g., protocol-mandated procedures, invasive tests, or change in existing therapy), study treatment or Novartis concomitant medication must be recorded from the time a subject consents to participate in the study up to and including any follow-up contact. All SAEs will be reported to Coordinating Center within 24 hours, as indicated in Section 8.5.1.

After discontinuation of study treatment, the investigator will monitor all AEs/SAEs that are ongoing until resolution or stabilization of the event or until the subject is lost to follow-up. At any time after 30 days the investigator may report any AE that they believe possibly related to study treatment.

8.5.1. Prompt Reporting of SAEs and Other Events

Serious adverse events (SAEs), pregnancies, and liver function abnormalities and any other events meeting pre-defined criteria will be reported promptly by the investigator on a Vanderbilt Serious Adverse Event Form and the centralized electronic case report form called ON-line Clinical Oncology Research Environment = Oncore [REDACTED] as described (Table 18) in the following table once the investigator determines the event meets the protocol definition for that event. SAEs should also be sent to Novartis and the NCCN as listed below:

All Events must be reported to Novartis within 24 hours of learning of its occurrence. Information about all SAEs is collected and recorded on a Serious Adverse Event Report Form; all applicable sections of the form must be completed in order to provide a clinically thorough report. The investigator must assess and record the relationship of each SAE to each specific study treatment (if there is more than one study treatment), complete the SAE Report Form in English, and send the completed, signed form by fax to [REDACTED] [REDACTED] within 24 hours to the oncology Novartis DS&E department with the provided FAX cover sheets and to NCCN via email to [REDACTED]

CONFIDENTIAL

Table 18 Rules for Reporting SAE, Cardiovascular, Pregnancy and Liver Function Abnormalities

Type of Event	Initial Reports		Follow-up Information on a Previous Report	
	Time Frame	Documents	Time Frame	Documents
All SAEs	24 hours	SAE data collection tool	24 hours	Updated SAE data collection tool
“CV events” and/or “death”	Initial and follow up reports to be completed within one week of when the cardiovascular event or death is reported	“CV events” and/or “death” data collection tool(s) if applicable	Initial and follow up reports to be completed within one week of when the cardiovascular event or death is reported	Updated “CV events” and/or “death” data collection tool(s) if applicable
Pregnancy	2 Weeks	Pregnancy Notification Form	2 Weeks	Pregnancy Follow-up Form
Liver chemistry abnormalities:				
ALT ≥3 times ULN and bilirubin ≥2 times ULN (>35% direct) (or ALT ≥3 times ULN and INR >1.5, if INR is measured) ^c	24 hours ^a	SAE data collection tool; Liver Event eCRF and liver imaging and/or biopsy eCRFs if applicable ^b	24 hours	Updated SAE data collection tool. Updated Liver Event eCRF ^b
ALT ≥5 times ULN; ALT ≥3 times ULN with hepatitis or rash or 3 times ULN ≥4 weeks	24 hours ^a	Liver Event eCRF ^b	24 hours	Updated Liver Event eCRF ^b
ALT ≥3 times ULN and <5 times ULN and bilirubin <2 times ULN	24 hours ^a	Liver Event eCRF does not need to be completed unless elevations persist for 4 weeks or subject cannot be monitored weekly for 4 weeks ^b		

- a. Coordinating Center is to be notified at onset of liver chemistry elevations to discuss subject safety.
- b. Liver event documents should be completed as soon as possible
- c. INR measurement is not required; if measured, the threshold value stated will not apply to subjects receiving anticoagulants.

CONFIDENTIAL

8.5.2. Regulatory reporting requirements for SAEs

Prompt notification of serious adverse events (SAEs) by the investigator to the Coordinating Center is essential so that legal obligations and ethical responsibilities towards the safety of subjects are met. All serious adverse events must be reported to the Coordinating Center within 1 business day after the treating institution becomes aware of the event. Events should be reported using the Vanderbilt Serious Adverse Event Form.

Follow-up information must also be reported within 1 business day of receipt of the information by the investigator.

The Coordinating Center has a legal responsibility to notify the local regulatory authority, the FDA and other regulatory agencies about the safety of a product under clinical investigation. The Coordinating Center will comply with country specific regulatory requirements relating to safety reporting to the regulatory authority, institutional review board (IRB)/ethics committee (EC) and investigators.

Investigator safety reports are prepared for suspected unexpected serious adverse reactions according to local regulatory requirements and Novartis policy and are forwarded to investigators as necessary.

An investigator who receives an investigator safety report describing a SAE(s) or other specific safety information (e.g., summary or listing of SAEs) from Novartis will file it with the IB and will notify the IRB/EC, if appropriate according to local requirements.

Food and Drug Administration (FDA)

In this trial, unexpected adverse events believed to be definitely, probably, or possibly related to the medications will be reported to the Food and Drug Administration via MedWatch Form 3500A Mandatory Reporting Form (using the online form available at: <http://www.fda.gov/downloads/Safety/MedWatch/HowToReport/DownloadForms/UCM082728.pdf> by telephone [name]; or by fax [name] using form available at: <http://www.fda.gov/Safety/MedWatch/HowToReport/ucm085692.htm>).

The Coordinating Center will be responsible for correspondence regarding adverse events with the FDA for all participating sites.

9. LIVER CHEMISTRY FOLLOW-UP PROCEDURES

9.1. Liver Chemistry Testing Procedures

For subjects meeting any of the liver chemistry stopping criteria in Section 3.10.1, make every attempt to carry out the **liver event follow-up assessments** described below:

- Viral hepatitis serology, including:
 - Hepatitis A IgM antibody
 - Hepatitis B surface antigen and Hepatitis B Core Antibody (IgM)

CONFIDENTIAL

- Hepatitis C RNA
- Cytomegalovirus IgM antibody
- Epstein-Barr viral capsid antigen IgM antibody (or if unavailable, then obtain heterophile antibody or monospot testing)
-
- Serum creatinine phosphokinase (CPK) and lactate dehydrogenase (LDH).
- Fractionate bilirubin, if total bilirubin ≥ 2 X upper limit of normal (ULN).

CONFIDENTIAL

- Obtain a complete blood count (CBC) with differential to assess eosinophilia.
- Record the appearance or worsening of clinical symptoms indicative of hepatitis or hypersensitivity, such as fatigue, nausea, vomiting, right upper quadrant pain or tenderness, fever, rash or eosinophilia as relevant on the AE eCRF.
- Record the use of concomitant medications, including acetaminophen, herbal remedies or any other over the counter (OTC) medications, or any putative hepatotoxins, on the concomitant medication eCRF.
- Record alcohol use on the liver event alcohol intake eCRF.

The following assessments are required for subjects with ALT ≥ 3 X ULN and bilirubin ≥ 2 X ULN ($>35\%$ direct) but are optional for other abnormal liver chemistries:

- Anti-nuclear antibody, anti-smooth muscle antibody, and Type 1 anti-liver kidney microsomal antibodies.
- Liver imaging (ultrasound, magnetic resonance imaging [MRI] or computed tomography [CT]) to evaluate liver disease.

9.2. Liver Chemistry Monitoring Criteria

For subjects with ALT ≥ 3 X ULN **but** <5 X ULN **and** bilirubin <2 X ULN, without symptoms indicative of hepatitis or rash, and who can be monitored safely for 4 weeks, the following actions should be taken:

- Notify the Medical Monitor within 24 hours of learning of the abnormality to discuss subject safety.
- Continue administration of study drug(s).
- Evaluate liver chemistries (ALT, AST, alkaline phosphatase, bilirubin) weekly until they resolve, stabilize or return to within baseline levels.
- If at any time the subject meets any of the liver chemistry stopping criteria 1 to 5 (Section 3.10.1), then proceed as described in Section 9).
- If, after 4 weeks of monitoring, ALT <3 X ULN and bilirubin <2 X ULN, then monitor subjects twice monthly until liver chemistries normalize or return to within baseline values.

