3.10. Dose Modifications for Trametinib and supportive care

3.10.1. Liver Chemistry Stopping Criteria

Liver chemistry threshold stopping criteria have been designed to assure subject safety and to evaluate liver event etiology during administration of study treatment(s) and the follow-up period. Study treatment(s) will be stopped if any of the following liver chemistry stopping criteria is/are met:

1. Alanine aminotransferase (ALT) ≥ 3 X (times) upper limit of normal (ULN) and bilirubin ≥ 2 Xs ULN (or ALT ≥ 3 X ULN and international normalization ratio [INR] > 1.5)

NOTE: Serum bilirubin fractionation should be performed if testing is available. If fractionation is unavailable, urinary bilirubin is to be measured via dipstick (a measurement of direct bilirubin, which would suggest liver injury).

2. ALT ≥ 5 X ULN.
3. ALT ≥ 3 X ULN if associated with the appearance or worsening of rash or hepatitis symptoms (fatigue, nausea, vomiting, right upper quadrant pain or tenderness, or jaundice) or hypersensitivity (such as fever, rash or eosinophilia).
4. ALT ≥ 3 X ULN persists for ≥ 4 weeks.
5. ALT ≥ 3 X ULN and cannot be monitored weekly for 4 weeks.

Subjects with ALT ≥ 3 X ULN **and** < 5 Xs ULN **and** bilirubin < 2 X ULN, who do not exhibit hepatitis symptoms or rash, can continue study treatment(s) as long as they can be monitored weekly for 4 weeks. As with other causes of dose holding, discussion with the medical monitor is required if trametinib is held for > 21 days. See following section for details on weekly follow-up procedures for these subjects.

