Appendix 5: Liver Safety Drug Restart Guidelines

Drug restart may be considered for a subject exhibiting compelling benefit for a critical medicine following drug-induced liver injury, if there is favorable benefit: risk ratio and no alternative medicine available.

Background Information on Drug Restart/Rechallenge

Following drug-induced liver injury, **drug restart or rechallenge is associated with a 13% mortality across all drugs in prospective studies.**¹ Clinical outcomes vary by drug, with nearly 50% fatality with halothane readministered in one month of initial injury. However, some drugs seldom result in recurrent liver injury or fatality. Risk factors for a fatal drug restart/rechallenge outcome include: hypersensitivity¹ with initial liver injury (e.g. fever, rash, eosinophilia), jaundice or bilirubin \geq 2xULN or INR $>$ 1.5 suggesting severe liver injury, prior IP-related severe or fatal drug restart/rechallenge^{2,3} or evidence of drug-related preclinical liability / mitochondrial impairment³.

Drug Restart/Rechallenge Process (also see Figure 1)

1. Principal Investigator (PI) requests consideration of drug restart for a subject receiving compelling benefit from a critical or life-saving drug, who exhibits liver chemistry elevation meeting subject stopping criteria, with no alternative treatment.
2. Medical Monitor & Clinical Safety Physician to review the subject's restart/rechallenge risk factors & complete checklist (Table 1).

Table 1. Checklist for drug restart/rechallenge for critical medicine		
(Following drug-induced liver injury, drug rechallenge is associated with 13% mortality across all drugs in prospective studies)		
	Yes	No
Compelling benefit of the investigational product (IP) for this subject and no alternative therapy. Provide brief explanation:		
Relative benefit-risk favorable for drug restart/rechallenge , after considering the following high risk factors:		
• Initial liver injury event included:		
– fever, rash, eosinophilia, or hypersensitivity		
– or bilirubin \geq 2xULN (direct bilirubin $>$ 35% of total)		
• Subject currently exhibits ALT \geq 3xULN, bilirubin \geq 2xULN (direct bilirubin $>$ 35% of total, if available), or INR \geq 1.5		
• Severe or fatal restart/rechallenge has earlier been observed with IP If yes, please provide brief explanation:		

[figure not shown]
CONFIDENTIAL

• IP associated with known preclinical hepatic liability/ injury		
--	--	--

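### The hypersensitivity trigger in liver stopping criterion 3 is missing from both continuation rules and from Table 18, so a narrow group of subjects meets the stop and the continue wording together and falls in a row that waives the Liver Event eCRF.

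*Combined protocol and SAP*

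**What the plan says.** Section 3.10.1 opens with a plain rule: "Study treatment(s) will be stopped if any of the following liver chemistry stopping criteria is/are met". Criterion 3 applies at ALT of at least 3 x ULN and has three limbs, any one of which is enough:

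- new or worsening rash;
- "hepatitis symptoms (fatigue, nausea, vomiting, right upper quadrant pain or tenderness, or jaundice";
- "or hypersensitivity (such as fever, rash or eosinophilia".

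For a subject who meets a criterion, Section 3.10.1.1 requires immediate permanent withdrawal from treatment and completion of the liver event eCRFs. Section 6.3 also lists the 3.10.1 criteria among the reasons why treatment ends.

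Three other places deal with subjects whose ALT is at least 3 but below 5 x ULN and whose bilirubin is below 2 x ULN:

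- The closing paragraph of 3.10.1 says that subjects "who do not exhibit hepatitis symptoms or rash, can continue study treatment(s) as long as they can be monitored weekly for 4 weeks".
- Section 9.2 covers subjects "without symptoms indicative of hepatitis or rash, and who can be monitored safely for 4 weeks" and directs that study drug be continued. Its fourth bullet adds that a subject who meets any of criteria 1 to 5 is to be handled as described in Section 9.
- Table 18 in Section 8.5.1 requires the Liver Event eCRF for "ALT ≥3 times ULN with hepatitis or rash", among other triggers. Its next row, for ALT 3 to below 5 x ULN with bilirubin below 2 x ULN, waives that form unless the elevation lasts 4 weeks or weekly monitoring is not possible.

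**The concern.** Criterion 3 has a hypersensitivity limb, and none of the three places that sort subjects by ALT band repeats it. The omission cannot be read as shorthand. Fever and eosinophilia are not in the list of hepatitis symptoms, and Sections 3.10.1.1 and 9.1 name hepatitis and hypersensitivity as separate things to record.

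Two things are at stake. The first is consistent handling: a site that reads criterion 3 and a site that reads the continuation paragraph can reach opposite conclusions about the same subject. The second is data capture: the table that sites use to decide which form to complete tells them that the liver form is not needed for an event for which 3.10.1.1 requires it.

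**Working it through.** The documents give no figure to reproduce and no arithmetic applies. The check traces one test case through each rule.

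**Test case.** ALT 4 x ULN; bilirubin below 2 x ULN; INR not above 1.5; new fever or eosinophilia; no rash; no fatigue, nausea, vomiting, right upper quadrant pain or tenderness, or jaundice; elevation present for less than 4 weeks; weekly monitoring possible. These conditions rule out criteria 1, 2, 4 and 5, so only criterion 3 is in play.

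| Place | Findings named | Result for the test case |
|---|---|---|
| 3.10.1, criterion 3 | rash; hepatitis symptoms; hypersensitivity | stop |
| 3.10.1.1 | any stopping criterion met | permanent withdrawal; liver event eCRFs required |
| 3.10.1, closing paragraph | hepatitis symptoms; rash | wording allows continuation |
| 9.2, entry condition and second bullet | hepatitis symptoms; rash | condition met, so continue |
| 9.2, fourth bullet | criteria 1 to 5 by reference | leave the monitoring path and proceed under Section 9 |
| Table 18, row requiring the Liver Event eCRF | hepatitis; rash; persistence for 4 weeks; ALT at least 5 x ULN | not met |
| Table 18, row for ALT 3 to below 5 x ULN | none, apart from two exceptions (4-week persistence, no weekly monitoring) | met, so the eCRF is waived |

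**Stop or continue.** Criterion 3 and the two continuation wordings overlap for this subject. The fourth bullet of 9.2 reduces the overlap, because it brings in criterion 3 with all its limbs. It then points to Section 9. There, 9.1 lists follow-up tests, 9.2 is the monitoring path just left, and the only explicit instruction to stop is in 9.4, for subjects whose drug was restarted after an unrelated liver event. The stop itself is in 3.10.1 and 3.10.1.1. The closing paragraph of 3.10.1 has no reference back to the criteria.

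**Liver Event eCRF.** Section 3.10.1.1 requires it and Table 18 waives it. Table 18 contains no reference back to criterion 3, so nothing in the text settles this second conflict.

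**Who is affected.** Rash is named everywhere. The gap therefore concerns only fever, eosinophilia or another hypersensitivity sign that occurs without rash and without a listed hepatitis symptom.

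**The case against.** The strongest reply is that the protocol, read as a whole, already resolves the treatment question. The fourth bullet of 9.2 applies at any time and names criteria 1 to 5. Section 3.10.1 says that any one of them stops treatment, and 6.3 says so again. Both routes also require the Medical Monitor to be told within 24 hours, so a site would not decide alone. This has force: on the text, the stop reading is the better supported one. It does not remove the problem, because the reader has to infer it past a pointer to the wrong section, and the 3.10.1 closing paragraph has no such safeguard. It also leaves the Table 18 conflict untouched. The word permanently is itself qualified, since 9.3 and Appendix 5 allow restart with approval.

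A reader might draw three stronger conclusions that the documents do not support.

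- *That eosinophilia could go unseen for a whole 28-day cycle.* The weekly panel in 9.2 contains no differential, and 9.1 asks for one only once a stopping criterion is met: "Obtain a complete blood count (CBC) with differential to assess eosinophilia". However, 3.10.1.1 asks for the same test in all subjects with ALT at least 3 x ULN, and the 3.10.1 continuation paragraph sends continuing subjects to that section. Table 14 adds hematology on Day 15 of Cycle 1 and more often as clinically warranted.
- *That Appendix 5 marks hypersensitivity as a risk factor for death in any subject who stays on drug.* The sentence begins "Risk factors for a fatal drug restart/rechallenge outcome include". It concerns re-exposure after liver injury, not uninterrupted dosing.
- *That liver stops of this kind could be missing from the safety data.* Section 8.3 requires an AE or SAE record for a result that leads to discontinuation, reduction or interruption. Section 6.3 requires the reason for discontinuation in the eCRF, and 3.10.1.1 puts hypersensitivity signs on the AE eCRF. Both Table 18 rows carry the 24-hour report.

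**Conclusion.** The point stands as an internal inconsistency in a liver safety rule and in the table that governs its reporting. For ALT at least 3 and below 5 x ULN, bilirubin below 2 x ULN, and fever or eosinophilia without rash or a listed hepatitis symptom, the stop rule and the wording of both continuation rules are met together. The 9.2 back-reference favours stopping but is incomplete. Separately, and without any resolving text, Table 18 waives a form that 3.10.1.1 requires. What can be lost is the liver-specific detail on that form, not the event.

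The size is limited. The affected group is narrow and the documents give no frequency for it, so no expected count can be stated. Sample size, error rates and the primary response analysis are untouched. The conclusion assumes that the hepatitis symptom list in criterion 3 also defines the phrase where it is used without a list in the continuation paragraph, in 9.2 and in Table 18. If those places are meant to use a wider definition that includes fever or eosinophilia, the protocol does not say so.

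**What to change.** - Reconcile criterion 3, the closing paragraph of 3.10.1, the entry condition of 9.2 and Table 18 so that all four use one list of accompanying findings. The simplest form is to define the list once and have the other three places refer to it.
- Point the fourth bullet of 9.2 to 3.10.1 and 3.10.1.1 instead of Section 9.
- Make the Liver Event eCRF requirement in Table 18 follow the same list, so that it agrees with 3.10.1.1.

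Which findings belong on the list, and so stop treatment, is a decision for the sponsor's clinicians; no view on it is offered here. The cost is protocol wording and an edit to Table 18, with no added visits or tests and no change to the statistical analysis.

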9.3. Drug Restart/Rechallenge Following Liver Events that are Possibly Related to Study Drug(s)

Approval by the Medical Monitor to restart/rechallenge study drug(s) may be considered where:

- The subject is receiving compelling benefit, the benefit exceeds the risk, and no effective alternative therapy is available. Approval of restart/rechallenge by the Institutional Review Board (IRB) or Independent Ethics Committee (IEC) must be obtained, as required.

CONFIDENTIAL

- If the restart/rechallenge is approved by Coordinating Center in writing, then the subject must be provided with a clear description of the possible benefits and risks of administration of study drug(s), including the possibility of a recurrence, a more severe liver injury or death.
- The subject must also provide signed informed consent specifically for the study drug(s) restart/rechallenge. Documentation of the informed consent must be recorded in the subject's study chart.
- Study drug(s) must be administered at the dose specified by the Medical Monitor.
- Subjects approved by the Coordinating Center for restart/rechallenge of study drug(s) must return to the clinic twice a week for evaluation of liver chemistry tests until stable liver chemistries have been demonstrated and laboratory monitoring may resume per protocol.

9.4. Drug Restart Following Transient, Resolving Liver Events Not Related to Study Drug(s)

Approval by the Medical Monitor to restart study drug(s) may be considered where:

- Liver chemistry abnormalities have a clear underlying cause (e.g., biliary obstruction, hypotension) and liver chemistries have improved to normal or are within 1.5 X baseline and ALT <3X ULN. Approval of restart by the Institutional Review Board (IRB) or Independent Ethics Committee (IEC) may be required.
- If the restart/rechallenge is approved by Coordinating Center in writing, then the subject must be provided with a clear description of the possible benefits and risks of administration of study drug(s), including the possibility of a recurrence, a more severe liver injury or death.
- The subject must also provide signed informed consent specifically for the study drug(s) restart/rechallenge. Documentation of the informed consent must be recorded in the subject's study chart.
- Study drug(s) must be administered at the dose specified by the Medical Monitor.
- Subjects approved by the Coordinating Center for restart/rechallenge of study drug(s) must return to the clinic once a week for evaluation of liver chemistry tests until stable liver chemistries have been demonstrated and laboratory monitoring may resume per protocol.
- If protocol-defined stopping criteria for liver chemistry abnormalities are met, study drug(s) administration must stop.

CONFIDENTIAL

